## **5.0 ANALYSIS OUTCOMES**

### **5.1 Primary Outcome**

1. Safety - Adverse events (AEs) and serious adverse events (SAEs) reported by physicians in the medical records (eg. incidence of any injection site reaction) during and after treatment with ENANTONE.
2. Effectiveness - Regression or no progression in Tanner staging during and after treatment with ENANTONE

### **5.2 Secondary Outcome**

1. LH and FSH suppression to prepubertal level during and after treatment with ENANTONE
2. Estradiol or testosterone level suppression to prepubertal level during and after treatment with ENANTONE
3. Decrease in the ratio of bone age to chronological age (BA/CA ratio) during treatment with ENANTONE

### **5.3 Additional Outcome**

- Increase in predicted adult height during and after treatment with ENANTONE
- Change from baseline in standard laboratory tests during and after treatment with ENANTONE
- Incidence of polycystic ovarian syndrome during and after treatment with ENANTONE
- Evaluation of long term effect on reproduction
  - Menstruation cycles (females)
  - Pelvic measurement
  - Sexual characteristic examination
  - Hormonal measurements
  - $\beta$ -HCG (females)
  - Pregnancy
- Change from baseline in bone mineral density (BMD) during and after treatment with ENANTONE.
- Change from baseline in body mass index (BMI) during and after treatment with ENANTONE.

## **6.0 DETERMINATION OF SAMPLE SIZE**

This retrospective study will analyze data from medical records of CPP subjects (from approximately 100 subjects), from multiple centers across China. Eight medical facilities in China, from both northern and southern region of China will be selected for this study. Within each site, eligible subjects will be enrolled until the site's subject quota has been reached. This study is observational and data will be collected as part of routine clinical practice and the outcomes will be reported based on available data.. The protocol sample size, 300 has been revised to 100 subjects following review and approval of China's Center for Drug Evaluation (CDE).

## 7.0 METHODS OF ANALYSIS AND PRESENTATION

### 7.1 General Principles

Statistical analysis will be performed using SAS® software (SAS Institute, Inc., Cary, North Carolina) Version 9.2, or later.

Data will be associated and summarized by the following:

- ENANTONE treatment phase includes all data from the first dose of ENANTONE up to and including either 45 days, inclusive, after the last dose or date of first dose of a non-ENTANTONE GnRH agonist therapy (earliest case scenario)
- Follow-up phase includes all data after the above defined ENANTONE treatment phase. If the subject continued treatment for CPP with another GnRH agonist after ENANTONE, their data from the follow-up period will be reported separately from those who only received ENANTONE for the treatment of CPP.

Unless specified otherwise, all data summaries will be performed for the following groups: Male, Female and Total, and will be presented during the ENANTONE treatment phase and results during the follow-up phase. Continuous variables will be summarized including the number, the mean, the standard deviation, median, minimum and maximum. Categorical variables will be summarized including the number and percentage of subjects.

Confidence intervals will be reported as 2-sided 95%, unless otherwise stated.

Means and medians will be presented to 1 more decimal place than the recorded data and standard deviations (SDs) will be presented to 2 more decimal places than the recorded data. Confidence intervals about a parameter estimate will be presented using the same number of decimal places as the parameter estimate. Derived variables may exhibit excessive decimal precision therefore, derived variables may be rounded to a precision representative of the expected data and means, SD and individual values will be formatted in a similar manner as described above.

#### 7.1.1 Study Definitions of Baseline and Change from Baseline

Baseline, for the ENANTONE period, is defined as the last non-missing measurement prior to the first dose of ENANTONE treatment. Unless specified otherwise, baseline values for variables related to CPP will be limited to values collected no more than 3 months (93 days), inclusive, prior to the first dose of ENANTONE.

The change from baseline will be calculated for the treatment period by subtracting the baseline values from the individual post-baseline values. If either the baseline or post-baseline value is missing, the change from baseline is set to be missing as well.

Data from the follow-up period after completion of treatment period, will be analyzed separately and the baseline for the follow-up period will be defined as the first non-missing measurement after the last dose of GnRHa treatment (with either ENANTONE or another GnRHa).

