10.2.2 Variables to be Collected

The following variables may be collected and recorded on the CRF as are available in the subject's chart. At a minimum, data related to the primary and secondary endpoints should be collected. This includes data at time of diagnosis of CPP, at the beginning of the ENANTONE Treatment Phase, at the end of the ENANTONE Treatment Phase and at the most recent time in the Follow-up Phase.

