10.7 Data Analysis

The clinical effective therapeutic dose as well as safety and effectiveness data of leuprorelin acetate used for the treatment of CPP will be summarized primarily using descriptive statistics; however inferential methods may be used to provide covariate adjustment as well as an indicator of data strength. To support the study objectives the primary data summaries will be focused on the ENANTONE treatment phase and the follow-up phase. The definition of each of these phases will be developed in the SAP. If more than 5% of subjects have CPP treatment with a generic GnRHa after ENANTONE then complimentary safety summary tables will be presented on those data from that therapy.

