10.7.3 Effectiveness Analysis

Any inferential statistical analysis resulting in p-values will be reported for the purpose of identifying notable findings rather than any formal test of statistical significance. Unless specified otherwise, all point estimates will be estimated alongside a companion 95% CI.

The primary effectiveness outcome, percentage of subjects who have regression or no progression (ie, response to treatment) in Tanner staging at the end of the ENANTONE Treatment Phase will be analyzed using a Cochran-Mantel-Haenszel (CMH) test with sex as

strata variable and dose (high, low) as independent variable. The adjusted odds ratio and 95% CI will be provided from the CMH test along with two-sided p-value. The 95% CI for the percent will also be determined using Clopper-Pearson exact method, unadjusted for sex, will be provided for overall responder and for each sub-response (regression/ no progression) for all subjects and by sex. If the final data are incompatible with the above analyses, then another method, such as ordinary percentages with 95% CIs (example using Wald type CIs), may be used.

Additional CMH analyses with adjustment by other demographic variables may be performed where necessary. If the data in the treatment period permits, similar analysis as described above will be performed at year intervals from the initiation of treatment, ie, Year 1, Year 2, etc.

The above analyses methodology will be also applied to the following effectiveness outcomes, at the end of the treatment phase and at year intervals, if appropriate:

- Percentage of patients with LH suppression
- Percentage of patients with FSH suppression
- Percentage of patients with estradiol or testosterone level suppression to prepubertal level
- Percentage of patients with a decrease from baseline in the ratio of bone age to chronological age
- Percentage of patients with an increase from baseline in predicted adult height

Change from baseline for BMI at end of treatment phase will be analyzed. This analysis will also be performed at each year interval, as permitted by available data and where applicable, of the treatment phase.

The above analysis will be used for the following quantitative variables, with associated baseline value as covariate:

- Change from baseline in BMI during the follow up phase, at yearly intervals, with end of treatment phase BMI as baseline
- Change from baseline in BMD, at end of treatment phase and at yearly intervals

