- Change from baseline in BMD during the follow up phase, at yearly intervals with the end of treatment phase bone density as baseline
- Change from baseline in patient height, at end of treatment phase and at yearly intervals
- Change from baseline in patient height during the follow up phase, at yearly intervals with end of treatment phase height as baseline

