**Figure 4.a      Overview of Study Design**

(a) Baseline: First day of administration of ENANTONE.

(b) End of Follow-up: The day of last available follow-up data for the subject.

Prior to ENANTONE treatment initiation, all relevant data (specified in Protocol Section 10.2.3.1), including data pertaining to the diagnosis of CPP will be collected at all available time points.

The **ENANTONE Treatment Phase** is the period during which patients were treated with at least 9 continuous months of ENANTONE. All relevant data (specified in Protocol Section 10.2.2) will be collected at all available time points.

The **Follow-up Phase** is the period after the ENANTONE Treatment Phase up to the day of last available follow-up data for the subject. All relevant data (specified in Protocol Section 10.2.2) will be collected at all available time points after the ENANTONE Treatment Phase. At a minimum, the data from the most recent time point available in the medical record should be included so as to include data on long term follow-up of the subject. During the Follow-up Phase, a GnRHa Treatment Interval may apply to those patients who were treated with a GnRHa (either generic leuprorelin acetate or another GnRHa) after completing the minimum of 9 months therapy with ENANTONE for CPP; in this case, the dates of therapy with this other GnRHa should be noted in the case report form (CRF).

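### The SAP's follow-up baseline departs, undeclared, from the protocol's end-of-treatment baseline for BMI, BMD and height, and no origin is stated for follow-up months

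*SAP*

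**What the plan says.** SAP 7.1.1 gives one follow-up rule for every variable: "the baseline for the follow-up period will be defined as the first non-missing measurement after the last dose of GnRHa treatment", whether that treatment was ENANTONE or another agent. The same section caps the age of the pre-treatment baseline for CPP-related variables at 93 days, but puts no limit on the delay to the follow-up baseline.

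Protocol 10.7.3 fixes a different baseline for three variables:

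- BMI: "Change from baseline in BMI during the follow up phase, at yearly intervals, with end of treatment phase BMI as baseline"
- BMD: "Change from baseline in BMD during the follow up phase, at yearly intervals with the end of treatment phase bone density as baseline"
- Height: "Change from baseline in patient height during the follow up phase, at yearly intervals with end of treatment phase height as baseline"

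On the study phases, protocol 10.7 says: "The definition of each of these phases will be developed in the SAP". SAP 7.1 accordingly runs the ENANTONE treatment phase "up to and including either 45 days, inclusive, after the last dose or date of first dose of a non-ENTANTONE GnRH agonist therapy", whichever comes first. SAP 7.8.1 takes the final Tanner value recorded in that phase as the end-of-treatment result. For follow-up it refers only to an appropriate baseline, which it does not name.

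On timing, SAP 7.1.2 counts all study days from the first ENANTONE dose, and 7.1.3 applies the months of Table 1 to follow-up as well as to treatment. SAP 7.7 measures follow-up duration in ENANTONE-only subjects from the last dose.

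On data, protocol 10.2.2 asks, for primary and secondary endpoints, for records at diagnosis, at the start of treatment, "at the end of the ENANTONE Treatment Phase and at the most recent time in the Follow-up Phase". SAP 4.4 says "At a minimum, the data from the most recent time point available in the medical record should be included", just after stating that every available follow-up time point will be collected.

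SAP 7.13 declares one change from the protocol: the dose comparison, and with it the CMH test, is dropped.

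**The concern.** A follow-up table should show what happens once treatment ends, so its baseline should be the state in which the subject left treatment. A baseline taken from the first later record, however late, absorbs whatever happened before it. A subject with a single later record contributes nothing. For BMI, BMD and height the protocol had already settled this, and a reader of SAP 7.13 would not learn that the rule had changed.

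The month index raises a second problem. If follow-up months are counted from the first ENANTONE dose, one column mixes subjects who stopped recently with subjects who stopped years ago. If they restart at the last dose, the columns mean something else. Two programmers could place the same record in different months and both claim to follow the SAP.

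**Working it through.** **1. Which record each rule picks (ENANTONE-only subjects).** Days are counted from the last dose. The end-of-treatment-phase value is read as the last value in the phase, as 7.8.1 does for Tanner. Days 1–45 still belong to the treatment phase. Let k be the number of follow-up records (day 46 onward), and suppose that a treatment-phase value exists.

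| Records in days 1–45 | Protocol 10.7.3 baseline | SAP 7.1.1 baseline | Changes: protocol / SAP |
|---|---|---|---|
| none | last value on or before last dose | first follow-up record | k / k−1 |
| exactly one | that record | that record | k / k |
| two or more | latest of them | earliest of them | k / k |

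In the first row, k = 1, 2, 3 gives 1 versus 0, 2 versus 1 and 3 versus 2, and change before the first follow-up record is lost. In the third row the SAP baseline is earlier, so its follow-up change includes more of the early period.

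**2. Variables without a protocol follow-up baseline.** These are Tanner stage, predicted adult height and laboratory tests (SAP 7.8.1 and 7.8.3). If 7.1.1 is applied to them, the same arithmetic holds, but as a weakness of the SAP rule. Take a subject with only the 10.2.2 minimum of one end-of-treatment Tanner record and one latest follow-up record. If the first is dated on or before the last dose, that subject has k = 1 and no follow-up change.

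**3. Subjects who switch.** SAP 7.8 plans, if data permit, a segment for data during the other GnRHa. The 7.1.1 baseline comes after the last dose of any GnRHa, so every record in that segment precedes it. With an assumed 15 months on the other agent (15 × 30.44 = 457 days), the earliest possible baseline is more than 457 days after the ENANTONE phase ends.

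**4. Table 1 reproduced.** For Month 3j the window is 46 + 90(j−1) to 135 + 90(j−1). The target day is 365 × month / 12, rounded down. All 20 rows match; for Month 39, j = 13 gives 1126–1215 with target 1186.

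**5. Earliest follow-up day on the literal reading.** The SAP 7.7 duration is (phase end − first dose + 1)/30.44. With the first dose on day 1, at least 9 months requires a phase end on or after 9 × 30.44 = 273.96, that is day 274. Follow-up then starts on day 275 at the earliest, inside Month 9 (226–315). Months 3 and 6 end at day 225, so both are empty for every subject meeting the 9-month criterion. If the 9 months must be reached by the last injection, without the 45-day tail, the last dose is on day 274, the phase ends on day 319 and follow-up starts on day 320 (Month 12).

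**6. What one literal month contains.** Consider a record on study day 1186, with illustrative last-dose days:

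| Last dose (day) | Days since last dose | Months (÷ 30.44) | Month, literal | Month from last dose |
|---|---|---|---|---|
| 273 | 913 | 30.0 | 39 | 30 |
| 365 | 821 | 27.0 | 39 | 27 |
| 730 | 456 | 15.0 | 39 | 15 |
| 1095 | 91 | 3.0 | 39 | 3 |

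**The case against.** **The SAP may refine the protocol.** The protocol's abstract leaves details of variables and methods to the SAP, and the end of the treatment phase is itself an SAP definition. That is fair, but the protocol fixed this particular baseline for three variables. A different choice is allowed; leaving it out of 7.13 is the fault.

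**The minimum data set is a floor.** Both documents plan to collect all available time points, so subjects with a single follow-up record may be few. This stands: the frequency is unknown. A reader might also infer that the 1-versus-0 case describes BMI, BMD and height at that minimum. It does not, because the 10.2.2 minimum covers primary and secondary endpoints, and these three are neither. For them the loss depends on what the charts hold.

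**The effect is not one-directional.** With two or more records in days 1–45, the SAP rule keeps more early change than the protocol rule. This also stands.

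**The literal month origin is implausible.** Two permanently empty months, and the 7.7 duration counted from the last dose, suggest that a restart was meant. A reader should not infer that the sponsor intends to index follow-up from the first ENANTONE dose. But no passage states a restart or names its first day.

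**Non-progression might seem inflated.** A reader might infer that a Tanner baseline record would count as its own unchanged result. Nothing in the SAP says that it would.

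**Conclusion.** The point holds and should be fixed, within limits. For BMI, BMD and height, SAP 7.1.1 is an undeclared departure from protocol 10.7.3. For Tanner stage, predicted adult height and laboratory tests it is a weak rule if applied, not a departure. For the other-GnRHa segment, the only follow-up baseline defined comes too late to be used. The follow-up month origin is unstated, and the one origin available gives columns that are empty or mix very different times since the last dose.

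For an ENANTONE-only subject with a treatment-phase value and no record in days 1–45, the cost is one change value and all change before the first follow-up record. The total across about 100 subjects cannot be derived from the documents.

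Only descriptive follow-up tables are affected. Hormone suppression uses fixed cut-offs and is touched only through the month index. A reader might infer that the main effectiveness result is at risk. It is not: the end-of-treatment Tanner analysis, the adverse event rates and BA/CA do not use this baseline or these follow-up months.

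**What to change.** 1. **Baseline (7.1.1).** For ENANTONE-only follow-up and for the other-GnRHa segment, use the last non-missing value in the ENANTONE treatment phase as 7.1 defines it. This is the protocol rule for BMI, BMD and height. State it as an SAP choice for Tanner stage, predicted adult height and laboratory tests. Report the time from that record to the last dose, and flag values more than 93 days before it.
2. **Month origin (7.1.2–7.1.3).** Define follow-up day as record date minus date of last ENANTONE dose, with the last dose as day 0. ENANTONE-only follow-up then starts at day 46, the lower bound of Month 3, and Table 1 can be kept. For the other-GnRHa segment, count from its first dose (day 0) and add a window for days 0–45.
3. **Data after the other GnRHa.** Match baseline and origin. Months counted from the last dose of that agent should use the last value on or before that dose, declared as an SAP addition, with a window for days 1–45. Show change from the protocol's end-of-ENANTONE baseline separately, indexed from the end of ENANTONE.
4. **Declaration (7.13).** List the baseline rules and the move from yearly to 3-month intervals.

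If the sponsor prefers to keep 7.1.1, it should at least declare it in 7.13 and name a baseline for the other-GnRHa segment. The month origin has to be stated either way.

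The cost is SAP wording and derivation code. No new data are needed: inclusion criterion 4 already requires an end-of-treatment Tanner record, and the other variables are used as the charts provide them. The downside is that an older end-of-treatment value carries some on-treatment change into follow-up; the reported time gap makes this visible.

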### **7.1.2 Definition of Study Days**

Study Day 1 is defined as the date on which a subject is administered their first dose of ENANTONE. Other study days are defined relative to the Study Day 1 with Day 1 being Study Day 1 and Day -1 being the day prior to Study Day 1.

### **7.1.3 Definition of Study Visit Windows**

Unless otherwise specified, longitudinal data will be summarized at 3-month intervals, as indicated in Table 1 below. The Months defined below will be applied to both the ENANTONE and follow-up periods. If actual data exceed the limits as defined by Table 1 then the sequence will be carried forward to satisfy the actual data.

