**Table 1 Windowing for longitudinal data**

Month	Target Study Day	Lower (Day)	Upper (Day)
3	91	46	135
6	182	136	225
9	273	226	315
12	365	316	405
15	456	406	495
18	547	496	585
21	638	586	675
24	730	676	765
27	821	766	855
30	912	856	945
33	1003	946	1035
36	1095	1036	1125
39	1186	1126	1215
42	1277	1216	1305
45	1368	1306	1395
48	1460	1396	1485
51	1551	1486	1575
54	1642	1576	1665
57	1733	1666	1755
60	1825	1756	1845

When a subject has multiple usable records within a window then the record nearest the target day will be used, and when two are equal distant from the target day, different days, then the later will be used. Lastly, if multiple values are on the same day then mean value (if numeric data) or the mode (if categorical data) will be used.

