### **7.1.7 Conventions for Missing Other Analysis Dates**

In order to derive 3-month intervals for efficacy or safety analysis, the following methods can be used to impute missing or partial start dates:

- Start date month/year available and day missing:
  - If the month and year are the same as those in the first dose date of ENANTONE treatment or study day -93, then the first dose date or study day -93 is to be used to impute the start date.
  - If the month and/or year are different from those in the first dose date of ENANTONE treatment or study day -93, then first day of the month will be used for the start date.
- Start date year available and month/day missing:
  - If the year is the same as those in the first dose date of ENANTONE treatment or study day -93, then the first dose date or study day -93 is to be used to impute the start date.
  - If the year is not the same as the year of the first dose date of ENANTONE treatment or study day -93, set the start date as January 1.

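### Table 1's visit windows drift early against their own targets, and the SAP applies them to follow-up without stating the day from which follow-up is counted

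*SAP*

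**What the plan says.** - **Windows.** SAP 7.1.3 and Table 1 give a target day and limits for each 3-month visit from Month 3 (target 91, limits 46–135) to Month 60 (target 1825, limits 1756–1845). Beyond Month 60, "the sequence will be carried forward to satisfy the actual data". The same months serve both phases: "The Months defined below will be applied to both the ENANTONE and follow-up periods".
- **Choice within a window.** "When a subject has multiple usable records within a window then the record nearest the target day will be used"; ties go to the later record.
- **Day count.** SAP 7.1.2: "Study Day 1 is defined as the date on which a subject is administered their first dose of ENANTONE". No other origin is defined, and Table 1's target column is in study days.
- **Phases.** SAP 7.1 runs the treatment phase "up to and including either 45 days, inclusive, after the last dose", or to the first dose of another GnRH agonist if that is earlier. Follow-up is everything later.
- **Follow-up baseline.** SAP 7.1.1: "the baseline for the follow-up period will be defined as the first non-missing measurement after the last dose of GnRHa treatment", whether that dose was ENANTONE or another product.
- **Use.** SAP 7.8.1 asks for Tanner response at 3-month intervals during treatment and, where applicable, during follow-up. SAP 5.1 places Tanner response after treatment within the primary effectiveness outcome.

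**The concern.** A visit label should mean roughly the time it names, and two programmers working from the same SAP should fill the same rows. Table 1 fails the first test increasingly as months pass, because its limits and targets follow different steps. The nearest-record rule cannot repair this, since it chooses only among records already inside a window.

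The follow-up tables fail the second test. Once treatment has stopped, the reader wants time since stopping, but the only defined clock measures time since starting. Depending on the origin a programmer adopts, the same record lands in different rows. The follow-up baseline adds a further risk: it is itself a post-treatment record, so if it also fills a follow-up window it is compared with itself and scores as no progression.

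**Working it through.** **1. Drift in Table 1.** Inputs are the 20 printed rows. With k = month/3, every row reproduces as:

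- target = whole part of month × 365/12, giving steps of 91 or 92 days;
- lower limit = 46 + 90(k − 1), upper limit = 45 + 90k, giving steps of exactly 90 days.

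Window centre = (lower + upper)/2. At Month 60 this is (1756 + 1845)/2 = 1800.5, and 1825 − 1800.5 = 24.5.

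| Month | Target | Limits | Days before / after target | Target − centre | Days in row nearer an earlier target | Cumulative |
|---|---|---|---|---|---|---|
| 3 | 91 | 46–135 | 45 / 44 | 0.5 | 0 | 0/90 |
| 12 | 365 | 316–405 | 49 / 40 | 4.5 | 3 | 6/360 (1.7%) |
| 24 | 730 | 676–765 | 54 / 35 | 9.5 | 8 | 32/720 (4.4%) |
| 36 | 1095 | 1036–1125 | 59 / 30 | 14.5 | 13 | 78/1,080 (7.2%) |
| 60 | 1825 | 1756–1845 | 69 / 20 | 24.5 | 23 | 230/1,800 (12.8%) |

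The last two columns compare each day's distance to its assigned target with its distance to every other printed target. All 230 days carry a later label than their nearest target. Of these, 230 − 78 = 152 (66%) lie in Months 39–60. For example, day 1756 is 69 days before the Month 60 target and 23 days after the Month 57 target (1733), yet it counts for Month 60. Day 1850, 25 days after the Month 60 target, does not.

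The windows are contiguous, so no day within the table's range is lost or counted twice. If the 90-day step is what is carried forward (an assumption), the target first leaves its own window at Month 111: target 3376, limits 3286–3375.

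**2. Follow-up on the only defined clock.** Nine months at the SAP 7.7 divisor is 9 × 30.44 = 273.96, so 274 days.

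- Counted as in 7.7, with the 45-day tail included, the treatment phase covers days 1–274 and follow-up opens on day 275.
- Counted from first to last dose, the last dose is on day 275, the phase ends on day 275 + 45 = 320, and follow-up opens on day 321.

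Both exceed 225, the Month 6 upper limit. Months 3 and 6 therefore hold no follow-up record for any subject with at least 9 months of treatment. Subjects enrolled in breach of that criterion stay in the full analysis set (7.2) and could have one.

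**Sensitivity to the origin.** Take an illustrative ENANTONE-only subject with the last dose on Study Day 730 and a visit on Study Day 913:

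| Origin | Day of visit | Row |
|---|---|---|
| First ENANTONE dose | 913 | Month 30 (856–945) |
| Last dose | 913 − 730 = 183 | Month 6 (136–225) |
| First follow-up day, 776 | 913 − 776 + 1 = 138 | Month 6 |
| First post-dose measurement, assumed on day 820 | 913 − 820 + 1 = 94 | Month 3 (46–135) |

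**3. Baseline inside a window.** The post-baseline wording in 7.1.1 is limited to the treatment period; the follow-up paragraph has no counterpart. On a last-dose clock, a baseline before day 46 falls outside every window. One on or after day 46 can fill a window and be scored against itself.

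**The case against.** The strongest reply is that a last-dose clock is plainly meant.

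- SAP 7.1.4 treats the last ENANTONE date as comparably important for indexing data.
- SAP 7.7 measures follow-up duration from the last dose.
- SAP 7.8.1 ties treatment-phase intervals to the start of ENANTONE, then covers follow-up in a separate sentence that refers to the appropriate baseline.
- The 45-day tail meets the Month 3 lower limit of 46 on such a clock. Day 46 is also midway between days 1 and 91, so this is suggestive only.
- SAP 7.1.7, which sets date rules "In order to derive 3-month intervals for efficacy or safety analysis" and names only "the first dose date of ENANTONE treatment or study day -93", deals with partial dates and sets no window origin.

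Much of this stands. A reader might infer that follow-up rows will in fact run on the first-dose clock. On that clock the Month 39 row (days 1126–1215) could hold ENANTONE-only records from 46 to 1215 − 275 = 940 days after the last dose. The sections above make that reading unlikely to be intended, so this span is not an expected result.

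They still do not settle the clock. For subjects who switched, 7.1.4 names the last ENANTONE dose, while 7.1.1 uses the last dose of any GnRHa. SAP 7.7 uses one for ENANTONE-only subjects and the other for those who switched.

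It is also fair that drift is small early on, that every printed target lies inside its own window, and that an ENANTONE-only baseline within 45 days of the last dose cannot enter a follow-up window on a last-dose clock.

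**Conclusion.** The point holds in three parts. Table 1 is internally inconsistent. This is a matter of arithmetic: the effect is small in the first two years (4.4% of days to Month 24), reaches 24.5 days by Month 60, and worsens if the 90-day step is carried forward. The follow-up day count is defective as written: the stated origin gives empty early rows and mixes times off treatment in later ones, and the likely intended origin is nowhere stated. The exclusion of the follow-up baseline record needs to be made explicit.

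The percentages are shares of calendar days, not of records; the documents give no visit distribution. A reader might also infer that self-comparison materially inflates the no-progression rate in follow-up. The documents do not show how often the baseline would fall on or after day 46, so no size can be given.

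Only the descriptive 3-month tables are affected. The end-of-treatment Tanner result uses the last observation in the treatment phase, and the overall adverse event rates per 100 person-years do not use Table 1.

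**What to change.** 1. **Limits.** Set each limit midway between adjacent targets, with ties to the later visit: lower = (previous target + target)/2, rounded up; upper = next lower limit − 1. Keep 46 as the first lower limit. This gives Month 3 = 46–136, Month 6 = 137–227, Month 9 = 228–318, Month 12 = 319–410, Month 24 = 684–775, Month 36 = 1049–1140 and Month 60 = 1779–1870 (taking the next target as 1825 + 91 = 1916). Windows are then 91 or 92 days long and centred within 0.5 day of target. Extend beyond Month 60 by the same rule.
2. **Post-treatment origin.** Count follow-up days from the last GnRHa dose, ENANTONE or other, in line with the 7.1.1 follow-up baseline. State which date is Day 1.
3. **Segment on another GnRHa.** Give it its own origin and name its baseline, because the 7.1.1 follow-up baseline arises only after that segment has ended.
4. **Baseline record.** State that the record used as follow-up baseline is excluded from the follow-up windows.

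The cost is some SAP wording, a corrected Table 1 and a re-run of any interval tables already programmed. The first follow-up window will hold slightly fewer records, because a subject whose only record there is the baseline drops out of that row. No new data are needed.
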